10.1.1.7. Adverse Event Outcome

Investigators will be instructed to report to the Sponsor or its designee their assessment of the outcome of each AE (both serious and non-serious). Definitions for possible AE outcomes include:

- Recovered/Resolved: the event has improved or the patient recuperated;
- Recovered/Resolved with Sequelae: the patient recuperated but retained pathological conditions directly resulting from the disease or injury;
- Recovering/Resolving: the event is improving;
- Not Recovered/Not Resolved: the event has not improved or the patient has not recuperated;
- Fatal: termination of life as a result of an AE. There should be only one AE marked with this outcome;
- Unknown: not known, not observed, not recorded, or refused.

10.1.1.8. Adverse Event Tabulations

All AEs (serious and non-serious) occurring after completion of the informed consent process and before the end of study will be included and classified by system organ class (SOC) and preferred term (PT) using MedDRA^{*} v23.0. Date imputation algorithm from Section 5.7.15 will be employed to partial dates.

A data listing of all AEs, including pre-treatment AEs (as defined in Section 5.7.15), will be provided including verbatim term, SOC, PT, toxicity, relationship to mobilization (G-CSF or plerixafor), relationship to apheresis, relationship to conditioning, relationship to AVR-RD-02, relationship to study procedure, relationship to underlying disease, date/time and day of onset, date/time and day of resolution, duration, possible co-medication, treatment given to treat the adverse event, the outcome, whether the event was an SAE, and whether it led to withdrawal. The derived study onset period used to tabulate AEs by onset will also be included. AEs prior to G-CSF for Mobilization will be flagged on this listing. In addition, a separate listing of all serious AEs will be provided, with any SAEs prior to treatment (Mobilization) flagged.

Deaths, if any, will be listed for subject, date/time, primary cause and autopsy finding.

Listings will be sorted by subject identification number, onset date/time, SOC, and PT. If the onset date is completely missing, then these events will be presented first. If the onset date is missing a month or a day then partial dates for AEs will be imputed as per Table 3 to allow AEs to be sorted appropriately. Imputed dates will not be listed.

The AE tabulations, unless stated otherwise, will be based on TEAEs. Therefore, all pretreatment AEs will be excluded from the tabulations, unless stated otherwise. However, pretreatment AEs that worsen/increase in severity after G-CSF for Mobilization will be recorded as new AEs and consequently will be regarded as treatment emergent and thus will be included in the tabulations.

Descriptive statistical methods will be used to tabulate the TEAE data including both the number of subjects and number of events. TEAE tables including the number of events will be presented in the following order: number of subjects, (percentage of subjects) and [number of events].

TEAEs will be presented in descending order of frequency across all subjects.

When it is necessary to calculate percentages, the denominator will be the total number of subjects in the analysis population, unless otherwise stated, and the numerator will be the total number of subjects reporting a TEAE within the relevant category. For AEs by Onset, the denominator used for each study period will be the number of subjects who participated in the study period. For AEs by Causal Relationship, the denominator used will only include evaluable subjects (e.g., a subject can only be included in the Busulfan category if they underwent conditioning with busulfan).

For tabulations by SOC and PT, when tabulating the number of subjects, if a subject has repeated episodes of a particular TEAE, all episodes will be counted in the tabulation, however, a subject with multiple events will only be counted once within each SOC and PT. A subject with more than one type of AE in a particular SOC will be counted only once in the total of subjects experiencing AEs in that particular SOC. Since a subject could have more than one type of AE within a particular SOC, the sum of subjects experiencing AEs in that SOC could appear larger than the total number of subjects experiencing AEs in that SOC. Similarly, a subject who has experiencing AEs in an AE in more than one SOC will be counted only once in the total number of subjects experiencing AEs in that presented in descending order of frequency (i.e., order by the overall grouping in descending frequency for each SOC and also for each PT within each SOC; in each case where there are equal frequencies items would be ordered alphabetically).

For tabulations by severity, the maximum severity for each subject will be used. A missing severity will not be imputed, but a row labelled 'Missing' will be included. If a subject has multiple events with the same SOC or PT, they will be counted under the worst severity for the tabulation, but the events will be counted under the applicable severity category.

If a subject has repeated episodes of a particular TEAE, only the most severe episode, or the episode with the strongest causal relationship, will be counted in the tabulations.

Plots of cumulative AE counts over time will be produced, with study day on the x-axis presented relative to date of AVR-RD-02 infusion (Study Day 1) for the Infused Population and relative to date of (first) signing of ICF for the Safety Population. When using the Infused Population, vertical reference lines will be included to represent the study day the subjects received their AVR-RD-02 infusion and their first and last doses of busulfan. These cumulative AE plots will be repeated for AEs \geq Grade 3, and for AEs that are deemed possibly, probably or definitely related to busulfan. Where a single AE is captured multiple times due to changing severity, each change in Grade will contribute to the cumulative number of AEs for that subject.

If it is possible to identify such AEs, the plots will be repeated with the multiple events collapsed into a single AE occurrence (with the causality and maximum grade considered appropriately).

• Overall Summary of TEAEs

The summary will include number of subjects (percentage of subjects) [number of events] for subjects with:

- At least one TEAE
- TEAEs related* to G-CSF for Mobilization
- TEAEs related to Plerixafor
- TEAEs related to Apheresis
- TEAEs related to Anti-Convulsant
- TEAEs related to Busulfan
- TEAEs related to Auxiliary Medication(s) or associated procedure
 - Combine G-CSF for Mobilization, Plerixafor, Apheresis, Anti-Convulsant and Busulfan
- TEAEs related to AVR-RD-02 infusion
- TEAEs related to Study Procedures
- TEAEs related to Underlying Disease
- TEAEs leading to Withdrawal
- TEAEs leading to Discontinuation of the Study
- TEAEs leading to Death
- Each CTCAE Grade
- Any severe (CTCAE Grade \geq 3) TEAE
- Maximum CTCAE Grade
- At least one Treatment-Emergent SAE (TESAE)

* 'related' includes those with a deemed possible, probable or definite causal relationship

• AEs by Onset

AEs by SOC and PT will be tabulated using the onset date/time of each adverse event to assign each AE into a study period according to Section 5.7.15. The summary will include number of subjects (percentage of subjects) [number of events]. Note since Pre-Mobilization is included that these tabulations include all AEs as well as TEAEs, and the denominator used to calculate percentages will be the number of subjects who participated in the study period:

- Pre-Mobilization: started before first dosing of G-CSF for Mobilization
- Auxiliary Medications:
 - \circ Mobilization:
 - G-CSF: started (or worsened) on or after first dosing of G-CSF for Mobilization and before start of apheresis

• For any subject who received Mobilization twice, the study period between the start of the second Mobilization until the start of the second apheresis will be captured as Mobilization #2

o Apheresis:

- started (or worsened) on or after start of apheresis until the end of the last apheresis
- For any subject who received apheresis twice, the study period between the start of the second apheresis until the end of the second apheresis will be captured as Apheresis #2
- Post-Apheresis: started (or worsened) after the end of the last apheresis and before first dosing of anti-convulsant medication given for prophylaxis ahead of busulfan
 - For any subject who received Mobilization twice, the study period between the end of the first apheresis and the start of Mobilization #2 will be captured as Post-Apheresis
 - The study period between the end of the second apheresis and the first dosing of anti-convulsant medication given for prophylaxis ahead of busulfan will be captured as Post-Apheresis #2
 - For any subject, who received Mobilization but did not proceed to receive conditioning or AVR-RD-02, the study period after the end of Apheresis will be captured as Post-Apheresis
- Conditioning: started (or worsened) on or after first dosing of anti-convulsant medication given for prophylaxis ahead of busulfan and before date of AVR-RD-02 infusion
- AVR-RD-02 Infusion: started (or worsened) on or after the start of infusion of AVR-RD-02
- Post-AVR-RD-02 Infusion Follow-Up: started (or worsened) after the end of AVR-RD-02 infusion

• Serious Adverse Events

SAEs will be listed.

• TEAEs by SOC, PT and CTCAE Grade

A tabulation of TEAEs by SOC and PT will be presented for each CTCAE Grade 1 to 5, Grade ≥ 2 and \geq Grade 3. The column for \geq Grade 3 will be used to determine decreasing order of frequencies. The summary will include number of subjects (percentage of subjects) [number of events].

• AEs by Causal Relationship

AEs by Onset will be repeated using the deemed causal relationship (possible, probable or definite) to each auxiliary medication (G-CSF, plerixafor, busulfan, anti-convulsant), apheresis,

AVR-RD-02, or study procedure, in turn. The summary will include number of subjects (percentage of subjects) [number of events]. Note since Pre-Mobilization is included that these tabulations include all AEs as well as TEAEs, and the denominator used to calculate percentages will be the number of subjects who participated in the study period.

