5.7.15. Derivations for Adverse Events

A treatment-emergent adverse event (TEAE) will be any adverse event occurring after a subject has started auxiliary medications, i.e., started mobilization with G-CSF. This includes: i) any AE that emerges after start of mobilization with G-CSF (having been absent before start of mobilization with G-CSF) or ii) any AE that although present before G-CSF, worsens after start of mobilization with G-CSF (in this case, there will be a new AE entered after worsening).

Where the start date/time of an AE is partial or missing and the end date/time is on or after the date/time of start of mobilization with G-CSF, or both the start and end dates/times are missing, then a "worst-case" scenario will be assumed, thus the AE is assumed to have occurred after the start of mobilization with G-CSF (i.e., treatment-emergent) unless a partial start or end date indicates otherwise. When partial dates are present in the data, both a partial start date and/or a partial end date will be evaluated to determine whether it can be conclusively established that the AE started prior to the start of mobilization with G-CSF or ended prior to the start of mobilization with G-CSF. If it cannot be conclusively established that the AE started prior to the start of mobilization with G-CSF based on the partial start and/or end dates, then the AE will be considered as treatment-emergent.

The following table presents an algorithm for the determination of whether a given AE will be considered treatment emergent or not:

Start date of AE	End date of AE	Action
Known	Known, Partial	If start date/time < start date/time of
	or Missing	mobilization with G-CSF, then not TEAE
		Otherwise, if start date/time \geq mobilization with
		G-CSF start date/time, then TEAE
Partial, but known	Known, Partial	Not TEAE
components show that it	or Missing	
cannot be on or after		
mobilization with G-CSF		
start date/time		
Partial, could be on or	Known	If end date/time < mobilization with G-CSF
after mobilization with		start date/time, then not TEAE
G-CSF start date/time		
OR Missing		If end date/time \geq mobilization with G-CSF
		start date/time, then TEAE
	Partial	Temporarily impute end date/time as latest
		possible date/time (i.e., 23:59 on last day of
		month if day and time unknown or 31st

 Table 3: Algorithm for Treatment Emergence of Adverse Events

Start date of AE	End date of AE	Action
		December 23:59 if day and month and time are
		unknown), then:

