The date and time of AEs are captured, as well as date and time for G-CSF, plerixafor, apheresis, busulfan and AVR-RD-02 infusion. Therefore, when assigning AEs to a study period, the time (HH:MM) of the onset (or worsening) of the AE will be compared to the time of the auxiliary medication or AVR-RD-02, e.g., on Day 1, an AE with onset time prior to the start time of AVR-RD-02 infusion will be assigned to the Conditioning study period. Where time is missing or incomplete, the AE will be assigned to the study period using the date alone, e.g., on Day 1, an AE on Day 1 with onset time missing will be assigned to the AVR-RD-02 infusion study period.

If an adverse event continues into subsequent periods it will only be counted in the period in which it first occurred, in order to avoid double counting.

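### One AE stored as several grade records can add one event or several to the TEAE tables, because the SAP's counting rules conflict and its collapse covers only the plots

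*SAP*

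**What the plan says.** - **Plots.** SAP 10.1.1.8 says of the cumulative plots: "Where a single AE is captured multiple times due to changing severity, each change in Grade will contribute to the cumulative number of AEs". It then adds: "If it is possible to identify such AEs, the plots will be repeated with the multiple events collapsed into a single AE occurrence". No other output has a stated collapse.
- **Tables.** Where event counts are shown, the TEAE tables present "number of subjects, (percentage of subjects) and [number of events" in brackets. This applies to the overall summary, AEs by Onset, TEAEs by grade and AEs by Causal Relationship.
- **Counting rules for the tables.** The same section first says that every repeated episode of a TEAE is counted, with the subject counted once per SOC and PT. For severity it puts the subject at the worst grade, "but the events will be counted under the applicable severity category". Its last sentence on the subject then says that, of repeated episodes, just the most severe or the most strongly related is counted. The SAP does not define an episode. Protocol 11.8.3 counts all occurrences as events.
- **Treatment emergence.** SAP 5.7.15 requires an AE that is new after G-CSF, or "any AE that although present before G-CSF, worsens after start of mobilization with G-CSF". Table 3 in that section compares the record's start date/time with the start of G-CSF and does not look at the direction of the grade change.
- **Periods.** SAP 5.7.15 and 10.1.1.8 place an AE in the period in which it started or worsened. SAP 5.7.15 also says: "If an adverse event continues into subsequent periods it will only be counted in the period in which it first occurred".
- **Recording.** Protocol 9.2.1.2 and SAP 10.1.1.5 leave the documentation of a severity change to the eCRF completion guidelines, which are not among the documents.

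**The concern.** The SAP recognises that records and AEs are not the same thing, but acts on this only in one set of plots. In the tables, two programmers following the text could report different event counts from the same data.

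Incidence and severity of AEs is a primary safety endpoint (SAP 2.2.2.1). SAP section 9 plans listings and figures for efficacy, so the AE tables are among the few summary tables in the report. Grade courses are also to be expected: the protocol anticipates deep but temporary marrow suppression after busulfan in every patient (6.2.2.2), and SAP 10.1.1 makes certain platelet, WBC and neutrophil grades AEs whether or not the investigator finds them clinically significant. At stake are the event counts, the by-period columns, and the TEAE status of AEs that were present before G-CSF and then improved.

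**Working it through.** The documents give no figure on this point, so there is none to reproduce. The check applies the stated rules to assumed cases.

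**1. Event count.** If every grade change opens a record, an AE with k grade changes has 1 + k records.

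Assumed AE (infusion on Day 1): Grade 2 on Day -2, Grade 3 on Day -1, Grade 4 on Day 5, Grade 3 on Day 14, Grade 2 on Day 20. Here k = 4, so there are 1 + 4 = 5 records. Treating each grade record as an episode:

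| Rule in SAP 10.1.1.8 | Events | Grade 3 or higher events |
|---|---|---|
| All episodes counted, each under its own grade | 5 | 3 (Grades 3, 4, 3) |
| Only the most severe episode counted | 1 | 1 |

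The mean number of grade changes per AE, m, is not given. Under the first rule the event count is (1 + m) times the number of AEs:

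| Assumed m | 0 | 0.5 | 1 | 2 | 4 |
|---|---|---|---|---|---|
| Multiplier | 1 | 1.5 | 2 | 3 | 5 |

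The second rule has its own fault. Two genuine recurrences of the same AE would count as 1 event, whereas the first rule and protocol 11.8.3 count 2.

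**2. Treatment emergence.** Assume an AE at Grade 3 before G-CSF that improves to Grade 2 and then Grade 1 afterwards, each entered as a new record.
- Table 3: both new records start after G-CSF, giving 2 TEAE records.
- Prose definition: the AE was present before and did not worsen, giving 0.

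If the subject has no other TEAE under that term, the TEAE subject count changes too.

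**3. Period columns.** The AE in step 1 has three records dated after infusion: one worsening (Grade 3 to 4, Day 5) and two improvements (Days 14 and 20). The number placed in Post-AVR-RD-02 Infusion Follow-Up depends on the rule:
- by the start date of each record: 3
- by the started-or-worsened wording: 1
- by the sentence that counts a continuing AE only in its first period: 0

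Under the first two, the subject also enters the number and percentage for that column.

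**4. What does not move.** For an AE that begins after G-CSF, the overall subject count stays the same (one per SOC and PT) and so does the maximum grade.

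**The case against.** The strongest reply is that the SAP's prose already guards against most of this. Its last counting sentence, taken literally, gives one event per TEAE. Treatment emergence needs new onset or worsening, periods are defined by start or worsening, and a continuing AE stays in its first period. Where the SAP says outright that a new AE is entered, the trigger is worsening. The study is descriptive and was stopped early, and every AE is listed with its onset, resolution and toxicity.

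Much of this stands, and it rules out two stronger readings:

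- **That the event counts are certainly inflated.** A reader might take the three mandatory cytopenias, assume courses of 2-3-4-3-2, 3-4-3 and 3-4-3, and arrive at 5 + 3 + 3 = 11 events for 3 AEs. The documents do not support this as an expected result. The courses are assumed, the SAP requires no record per grade, and one of the two counting rules gives 3.
- **That recovery from busulfan will be shown as new TEAEs after infusion.** The prose does not prescribe this. An AE that began after G-CSF is already a TEAE, so its improvement can at most be counted twice or put in the wrong period.

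The reply does not remove the defect. The last counting sentence contradicts those before it and speaks of repeated episodes, not of grade records of one AE. The continuation rule works only if records are linked, and the SAP gives no linking rule and makes even the plot collapse conditional: "If it is possible to identify such AEs".

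**Conclusion.** The SAP should be corrected on this point. Its rules give different event counts and period columns from the same data, and Table 3 disagrees with the definition that it is meant to implement.

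- **Event counts:** one AE with k grade changes adds 1 or 1 + k, depending on which sentence is followed. The overall effect cannot be stated without the mean number of grade changes.
- **TEAE status:** only AEs present before G-CSF that later improve are exposed.
- **Periods:** event counts and subject percentages by period can both be affected.

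The last two results, for a record that shows only improvement, assume that a fall in grade is entered as a new record. The plots' reference to each change in grade suggests this, but the eCRF guidelines would have to confirm it.

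**What to change.** 1. Replace the conflicting sentences in SAP 10.1.1.8 with one rule: genuine recurrences are separate events, and contiguous grade records of the same AE are one event at maximum grade and strongest causality. This extends the collapse from the plots to the tables. State how records are linked.
2. Add to Table 3 and to the period assignment that a record showing only a fall in grade is neither a new TEAE nor a new event in a later period. A pre-G-CSF AE that later worsens stays treatment-emergent, as now defined.
3. Keep a true worsening in the period in which it worsened, and reword the continuation sentence in SAP 5.7.15 so that it covers only continuation without worsening. Placing a linked AE in its first period alone would hide a worsening after infusion. Footnote that the period columns need not add up to the overall count.
4. Keep all records in the listings, and footnote any that cannot be linked.

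The cost is one derivation, some programming and smaller event counts.

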10.1.1. Presence of Replication Competent Lentivirus (RCL)

Results of the peripheral blood tests will be listed, with absence of RCL identified by a negative result. In case of confirmed positivity, any resulting RCL culture test results will be listed.

10.1.2. Identification of mononuclear cells with integration site profiles suggestive of aberrant clonal expansion(s)

Monitoring for aberrant clonal expansion (ACE) requires the clinical review of multiple datasets (e.g., routine clinical and laboratory surveillance, repertoire study, bone marrow examination, integration site analysis). Therefore, no summary tables focused solely on ACE will be produced. The results of the manual clinical review for ACE will be described in the summary documents with cross-reference to the relevant study listings and a separate integration site analysis report.

10.1.3. Clinical Laboratory Evaluations

The details of measurement of laboratory parameters are described in the study protocol. International System (SI) units will be used in all outputs.

Serum chemistry includes aspartate aminotransferase (AST), alanine aminotransferase (ALT), gamma-glutamyl transferase (GGT), amylase, lipase, alkaline phosphatase (ALP), lactate dehydrogenase (LDH), bilirubin, calcium, albumin, phosphate, magnesium, uric acid, and glucose.

Electrolytes include sodium, potassium, chloride, bicarbonate, blood urea nitrogen (BUN), and serum creatinine.

Hematology includes hematocrit, hemoglobin, platelet count, WBC count (total and differential), RBC count, and ANC.

All hematology, serum chemistry and urinalysis data including CFB will be listed. In these listings, sample collection data (e.g., collection times) for laboratory analysis and urinalysis data will be included, and individual data will be flagged with an "H" or an "L" for values that are higher or lower than their normal ranges, respectively, and any clinically significant (CS) and not clinically significant (NCS) records will be flagged.

For the listings of ALT and of AST, the following values will be flagged to indicate evidence of Drug-Induced Liver Injury:

- ALT or AST $> 8 \times ULN$
- ALT or AST $> 5 \times ULN$
 - In the CSR, an assessment will be made of whether ALT or AST remained above 5×ULN for more than 2 weeks
- ALT or AST $> 3 \times ULN$

 In the CSR, an assessment will be made of whether ALT or AST remained above 3×ULN with the appearance of fatigue, nausea, vomiting, right upper quadrant pain or tenderness, fever, rash, and/or eosinophilia (>5%)

For the listing of ANC values, a flag will indicate ANC $< 0.5 (10^9/L)$.

For the listing of platelet values, flags will indicate platelets $< 35 (10^{9}/L)$ and $< 20 (10^{9}/L)$.

For each laboratory parameter with a defined normal range, absolute values will be defined at each protocol-scheduled time point as low, normal, or high, and post-baseline values will be compared to the baseline value through shift tables.

In addition, one flag will be derived to identify whether the parameter had at least one value above the normal range at any time post-treatment, and another to identify whether the parameter had at least one value below the normal range at any time post-treatment. Subjects having both High and Low values relative to normal ranges at post-treatment visits for laboratory parameters will be counted in both the High and Low categories of the "Any visit post-treatment" row of related summary tables.

The denominator used in laboratory shift table summaries will only include evaluable subjects (i.e., those who have both a baseline and at least one post-baseline value recorded).

Individual subject data for the ratio of value to LLN for Hgb, HCT, ANC, Platelets, Reticulocytes and Leukocytes will be plotted vs. study week, with a line for each parameter on the same plot and one plot for each subject. Vertical reference lines will be included to represent the study day the subjects received their AVR-RD-02 infusion and their first and last doses of busulfan. A horizontal reference line will be included at 1.

Any available microscopic urinalysis will also be listed.

Partial thromboplastin time (PTT) and international normalized ratio (INR) will be listed.

Flow cytometric analysis of T and B cell counts as well as peripheral blood lymphocyte subsets (CD3, CD4, CD8, CD19, and CD16/56) will be listed.

